9.1.2.1 Primary

The primary outcome of this study is live birth. It is defined generally as the complete expulsion or extraction from a woman of a product of fertilization, after 22 completed weeks of gestational age; which, after such separation, breathes or shows any other evidence of life, such as heartbeat, umbilical cord pulsation or definite movement of voluntary muscles, irrespective of whether the umbilical cord has been cut or the placenta still attached or not (16).

Information on live birth will be obtained from the medical birth register in each country and the IVF register in Sweden. Only live births that can be linked to a given IVF/ICSI stimulation cycle included in the study will be considered. The live birth of multiples will be counted as one live birth in this study.

For the assessment of the primary objective and secondary objective 4, the different measures of live birth are defined as follows:

- LBR is the probability of a live birth after one initiated stimulation cycle, considering fresh embryo transfer.
- CLBR is the number of live births per initiated stimulation cycle, considering all fresh and subsequent frozen embryo transfers linked to that stimulation cycle and counting all live births from the same transfers.
- MC-CLBR is the probability of a live birth in up to five stimulation cycles, considering all fresh and subsequent frozen embryo transfers linked to each of those stimulation cycles, until the first live birth occurs.
- TTLB is the time (in number of cycles) until live birth in up to five stimulation cycles, considering all fresh and subsequent frozen embryo transfers linked to each of those stimulation cycles, until the first live birth occurs.

For the calculation of the above measures, refer to Section 9.7.3.3 (Table 7).

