9.1.2.2 Secondary

There are several secondary outcomes, which are connected to the secondary study objectives:

1. Clinical pregnancy is defined generally as pregnancy diagnosed by ultrasonographic visualization of one or more gestational sacs. It includes intrauterine pregnancy and clinically documented ectopic pregnancy (16). In this study, multiple embryos will be counted as one clinical pregnancy.

Intrauterine pregnancy will be ascertained in the IVF registers. Diagnosis and procedure codes used to ascertain ectopic pregnancy in the national patient registers are provided in Appendix 3 (Section 14.3.1).

For the assessment of secondary objective 1, clinical pregnancy is measured as CPR and CCPR, which are defined analogously to LBR and CLBR:

- CPR is the probability of a clinical pregnancy after one initiated stimulation cycle, considering fresh embryo transfer.
 - CCPR is the number of clinical pregnancies per initiated stimulation cycle, considering all fresh and frozen embryo transfers lined to that stimulation cycle and counting all clinical pregnancies from the same transfers.
2. Ongoing pregnancy is defined in this study as pregnancy still ongoing at 22 completed weeks of gestational age. It will be ascertained based on a record of miscarriage or induced abortion (before 22 completed weeks of gestational age), or gestational age at delivery in the national patient registers or the IVF register in Sweden. Multiples will be counted as one ongoing pregnancy.

For the assessment of secondary objective 1, ongoing pregnancy is measured as OPR and COPR, which are defined analogously to LBR and CLBR:

- OPR is the probability of an ongoing pregnancy after one initiated stimulation cycle, considering fresh embryo transfer.
- COPR is the number of ongoing pregnancies per initiated stimulation cycle, considering all fresh and frozen embryo transfers linked to that stimulation cycle and counting all ongoing pregnancies from the same transfers.

Only clinical pregnancies and ongoing pregnancies that can be linked to a given IVF/ICSI stimulation cycle included in the study will be considered.

3. Oocytes retrieved is defined generally as the total number of oocytes retrieved from an ovarian follicular aspiration following COS. Information on the number of oocytes retrieved will be ascertained in the IVF registers.

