9.7.2 Derived and Transformed Data

The data sources included for this study are national healthcare registers that are expected to have a comprehensive coverage and high-quality data. Thus, large amounts of missing data is not expected to be an issue in this study. In case of missing data, a missing data category will be added, and the number of observations and patients with missing data will be reported for each measured variable in the study. The handling of missing data will be described in more detail in the SAP.

The IVF registries may record some of study covariates related to patient characteristics (see Table 1, section 9.3.2), such as smoking status or BMI, only for the patient's first stimulation cycle. Thus, the covariate value from the patient's first stimulation cycle will be used also for the patient's subsequent cycles if the covariate values for the subsequent cycles are missing.

Any study variables and outcomes that are only recorded if an event occurs, such as live birth, are not considered missing. Also, any outcomes relying on the presence of a diagnostic code (i.e. ICD-10), such as OHSS, fit this definition.

Any derived and transformed data needed for conducting the statistical analysis will be described in the SAP.

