14.3 Additional Information

All code lists included below may be subject to amendment or revision during study conduct.

14.3.1 Outcome variables (Section 9.1.2): Diagnosis and Procedure Codes for Definition and Databases for Identification

Outcome	Code for identification ⁺	Comment	Source for identification
Primary outcome			
Live birth	N/A		DMBR, SMBR, Q-IVF
Secondary outcomes			
Clinical pregnancy	ICD-10: O00 NOMESCO procedure codes: MCB 00, LAA 20, LBC*	Intrauterine pregnancy ascertained in the DIVF and Q-IVF. ICD-10: Ectopic pregnancy NOMESCO procedures: laparotomy and delivery of extrauterine fetus, percutaneous or transvaginal injection into ovarian pregnancy, tube conserving operations for tubal pregnancy	DIVF, Q-IVF, DNPR, SNPR
Ongoing pregnancy	ICD-10: O03, O04, O05, O06 [#] NOMESCO procedure codes: LCH*	Delivery and gestational age at delivery ascertained in the DMBR and SMBR. For Sweden, miscarriage and induced abortion† will be ascertained in the SNPR and Q-IVF. ICD-10: spontaneous abortion, medical abortion, other abortion, unspecified abortion NOMESCO procedures: procedures related to termination of pregnancy	DMBR, SMBR, DNPR, SNPR, Q-IVF
Oocytes retrieved	N/A	Ascertained using information recorded in the DIVF and Q-IVF.	DIVF, QIVF
Embryos transferred			
Embryos cryopreserved			
Implantation			
Pregnancy loss	ICD-10: O03, O04, O05, O06 [#] NOMESCO procedure codes: LCH*	ICD-10: spontaneous abortion, medical abortion, other abortion, unspecified abortion NOMESCO procedures: procedures related to termination of pregnancy	DNPR, SNPR, Q-IVF

Outcome	Code for identification ⁺	Comment	Source for identification
		For Sweden, miscarriage and induced abortion† will be ascertained in the SNPR and Q-IVF.	

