Multiple pregnancy	ICD-10: O03, O04, O05, O06 [#] NOMESCO procedure codes: LCH*	Ascertained in the DIVF and Q-IVF based on ultrasonographic visualization of two or more gestational sacs. To capture multiple pregnancy with monozygotic twins, which share the same gestational sac, an algorithm will be defined. The algorithm will consider intrauterine pregnancy loss (miscarriage or induced abortion) before 22 completed weeks of gestational age and live or stillbirth after 22 completed weeks of gestational age. Thus, the algorithm accounts for reduction of multiple pregnancies. This will be particularly important for Denmark, as the DIVF does not record pregnancy outcome. For Sweden, however, the Q-IVF captures pregnancy outcome for each fetus, in case of multiple pregnancy. The algorithm will be detailed in the SAP. ICD-10: spontaneous abortion, medical abortion, other abortion, unspecified abortion NOMESCO procedures: procedures related to termination of pregnancy	DIVF, Q-IVF, DNPR, SNPR, DMBR, SMBR
Cycle cancellation	N/A	Ascertained using information recorded in the DIVF and Q-IVF.	DIVF, QIVF
OHSS	ICD-10: N98.1	ICD-10: Hyperstimulation of ovaries For Sweden, OHSS is recorded in the Q-IVF as a) requiring inpatient hospitalization with/without ascites drainage, or b) requiring ascites drainage in outpatient specialized care. In both countries, the national patient registers and the IVF registers will be used to ascertain information on OHSS.	DNPR, SNPR, Q-IVF
Treatment-associated costs	To be defined	Relevant ATC, procedure, ICD-10, and DRG codes (including associated costs/weights) and cost listings will be used to ascertain costs. These codes will be further detailed in the SAP.	RMPS, SPDR, DIVF, Q-IVF, DMBR, SMBR, DNPR, SNPR, cost listings‡

ATC: Anatomical Therapeutic Chemical; DIVF: Danish In-vitro Fertilization Register; DMBR: Danish Medical Birth Register; DNPR: Danish National Patient Register; DRG: diagnosis-related group; ICD-10: International Classification of Diseases, 10th revision; IVF: in vitro fertilization; N/A: not applicable; NOMESCO: Nordic Medico-Statistical Committee; Q-IVF: Swedish National Quality Registry of Assisted Reproduction; RMPS: Danish Register of Medicinal Product Statistics; SAP: statistical analysis plan; SMBR: Swedish Medical Birth Register; SNPR: Swedish National Patient Register; SPDR: Swedish Prescribed Drug Register.

Notes:

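### Intrauterine clinical pregnancy is taken only from the IVF registers, so a linked Danish delivery without an IVF-register pregnancy record counts in LBR and OPR but not in CPR or CCPR (minor)

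*Protocol*

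**What the plan says.** Section 9.1.2.2 gives a general definition, "Clinical pregnancy is defined generally as pregnancy diagnosed by ultrasonographic visualization of one or more gestational sacs", and includes documented ectopic pregnancy. It then fixes the sources: "Intrauterine pregnancy will be ascertained in the IVF registers", and for the ectopic part "Diagnosis and procedure codes used to ascertain ectopic pregnancy in the national patient registers are provided in Appendix 3". The table in Section 14.3.1 agrees: "Intrauterine pregnancy ascertained in the DIVF and Q-IVF". A note under that table treats a condition sourced from the IVF registers as present when those registers hold an entry for it.

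Live birth has different sources. Section 9.1.2.1 states: "Information on live birth will be obtained from the medical birth register in each country and the IVF register in Sweden". The only further condition is "Only live births that can be linked to a given IVF/ICSI stimulation cycle included in the study will be considered"; no scan or pregnancy entry is required. For ongoing pregnancy, Section 14.3.1 takes delivery and gestational age from the birth registers.

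Table 7 uses clinical pregnancies as the denominator for pregnancy loss (objective 5) and multiple pregnancy (objective 6). Section 9.4.1 says that DIVF does not hold pregnancy outcome. Section 9.4.2 says that the Swedish Q-IVF does.

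**The concern.** Every delivery was once a clinical pregnancy, so the three outcomes should be nested: live birth within ongoing pregnancy within clinical pregnancy. The protocol draws the widest of the three from a source that the narrower ones need not pass through, and it has no rule to restore the nesting.

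At stake are CPR and CCPR (objective 1), which would count some known deliveries as non-pregnancies, and the set of pregnancies in which loss and multiple pregnancy are assessed. The primary measures LBR, CLBR and MC-CLBR do not use the clinical-pregnancy variable and are not touched.

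**Working it through.** The protocol gives no figure to reproduce, so the check is of sources first and of possible size second.

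**Sources listed in Section 14.3.1**

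| Outcome | IVF registers | Patient registers | Birth registers |
|---|---|---|---|
| Clinical pregnancy | DIVF, Q-IVF | DNPR, SNPR (ectopic codes) | none |
| Ongoing pregnancy | Q-IVF | DNPR, SNPR | DMBR, SMBR |
| Live birth | Q-IVF | none | DMBR, SMBR |
| Pregnancy loss | Q-IVF | DNPR, SNPR | none |
| Multiple pregnancy | DIVF, Q-IVF | DNPR, SNPR | DMBR, SMBR |

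**Denmark.** Take a cycle with a delivery in the DMBR linked to it and no pregnancy entry in DIVF. It is a live birth and an ongoing pregnancy, since neither uses DIVF. It is not an intrauterine clinical pregnancy, since DIVF is the only Danish source for that. It therefore adds to LBR and OPR but not to CPR or CCPR. Table 6 and Section 9.7.3.4 analyse loss and multiple pregnancy per clinical pregnancy, so it also leaves those analyses. A loss recorded in the DNPR without a DIVF pregnancy entry leaves them in the same way.

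**Sweden.** Q-IVF is an IVF register and holds pregnancy outcome, so a delivery can be recognised inside the source named for clinical pregnancy.

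**Possible size for CPR.** All inputs are assumptions: true CPR C = 25% to 35%, share of clinical pregnancies lost L = 20%, the rest delivered, and share m of deliveries without a DIVF pregnancy entry.

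Observed CPR = C × [1 − (1 − L) × m] = C × (1 − 0.8m).

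| m | Relative understatement | Points at C = 25% | C = 30% | C = 35% |
|---|---|---|---|---|
| 0% | 0% | 0 | 0 | 0 |
| 1% | 0.8% | 0.20 | 0.24 | 0.28 |
| 2% | 1.6% | 0.40 | 0.48 | 0.56 |
| 5% | 4% | 1.0 | 1.2 | 1.4 |
| 10% | 8% | 2.0 | 2.4 | 2.8 |

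The cohort-level CPR would fall below LBR only if 1 − 0.8m < 0.8, that is m > 25%. Within the range shown, single cycles break the nesting but the rates keep their order.

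If losses lack the entry as often as deliveries, observed CPR is C × (1 − m). Adding linked deliveries brings it to C × (1 − L × m). At C = 30% and m = 5%, that is a move from 0.30 × 0.95 = 28.5% to 0.30 × 0.99 = 29.7%. The denominator is initiated cycles throughout, so for CPR and CCPR the addition only moves the estimate towards the truth.

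**Objectives 5 and 6.** Here the denominator is itself clinical pregnancies. Assume L = 20%, with the entry missing equally often (m) for losses and deliveries.

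- Numerator and denominator both from IVF-register pregnancies: 0.20(1 − m)/(1 − m) = 20%, unbiased.
- Births alone added to the denominator: 0.20(1 − m)/[0.20(1 − m) + 0.80]. At m = 5% this is 0.19/0.99 = 19.2%; at m = 10% it is 0.18/0.98 = 18.4%.

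The union rule that helps CPR therefore biases the loss rate downward if only births are added.

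**The case against.** The strongest reply is that the gap may be close to empty. Section 9.9.2 says that pregnancy measurements must be reported to DIVF and calls the study-period data electronic, complete and validated. Section 9.4.1 says that scan results, including sac counts, have been held since the 2006 improvements. That DIVF lacks pregnancy outcome says nothing about how completely scans are entered. This stands as a limit on size. It is not proof of completeness for this field: the reference given for the statement is a 1999 article on the register, which predates the addition of scan results.

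A second reply is that Section 9.1.2 allows linked registers to be used as needed, and that Section 9.7.2 leaves derivations to the SAP, which was not available. But the protocol itself names the sources for clinical pregnancy and omits the birth registers. For multiple pregnancy, by contrast, it adds births and defers an algorithm: "The algorithm will consider intrauterine pregnancy loss (miscarriage or induced abortion) before 22 completed weeks of gestational age and live or stillbirth". The specific text governs.

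A reader might also infer more than the protocol supports:

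- *That clinical pregnancy rests on the scan alone.* Ectopic pregnancies come from the patient registers, and Table 1 also lists a pregnancy test result or pregnancy indicator for deriving outcomes.
- *That Section 9.7.2 settles that no scan entry means no pregnancy.* Its sentence "Any study variables and outcomes that are only recorded if an event occurs, such as live birth, are not considered missing" concerns items recorded only when an event occurs; a scan result is a field that can be blank. The note in Section 14.3.1 is the better support.
- *That a twin birth can be in the numerator of objective 6 but not its denominator.* The stated unit is the clinical pregnancy, so such a case drops out altogether.
- *That the loss rate is inflated.* This holds only if deliveries lack the entry more often than losses, which nothing in the protocol shows.
- *That products are affected differently.* No passage shows this, and private or public clinic type is a propensity-score candidate.
- *That Sweden is equally exposed.* Besides holding pregnancy outcome, Q-IVF is reported to lose only 0.13% and 0.14% of fresh cycles to follow-up in two years.

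**Conclusion.** The mismatch of sources is real and fixed in the protocol text. As written, a linked Danish delivery without a DIVF pregnancy entry is a live birth and an ongoing pregnancy but not a clinical pregnancy, and it falls outside objectives 5 and 6. This rests on reading the Section 14.3.1 note in its natural sense, that without an entry the condition is treated as absent.

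The size is unknown. It is nil if DIVF is complete, and a relative understatement of CPR of 0.8% to 8% if 1% to 10% of deliveries lack the entry and 20% of pregnancies are lost, all assumed. No bias between products and no direction of bias in the loss or multiple-pregnancy rates is established. Only secondary outcomes are affected, so this is a minor point, worth making because the remedy is nearly free.

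**What to change.** Change Sections 9.1.2.2 and 14.3.1 as follows.

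- **CPR and CCPR:** count a clinical pregnancy when any of these is linked to the transfer: an intrauterine pregnancy in the IVF register, a recorded ectopic pregnancy, or a delivery (live or stillbirth) or ongoing pregnancy. Add the DMBR and SMBR to the listed sources. Report by product and country how many were found only through the birth register; that count also shows whether the gap matters.
- **Objectives 5 and 6:** do not add births alone. Either restrict numerator and denominator to IVF-register clinical pregnancies, or add linked deliveries and linked recorded losses together. State which.

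The cost is a few lines of text and one extra table row, since the birth linkage is already made for the primary outcome. The downside is a small departure from the strict ultrasound definition for cases found only through the birth register; the reported count makes it visible.

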9.2 Setting

9.2.1 Study Population

This study will comprise IVF/ICSI stimulation cycles and FET cycles linked to the same stimulation cycles among women who received rhFSH-alfa reference product, HP-hMG or rhFSH-alfa biosimilar products for COS. The countries of study are Denmark and Sweden. The study population will be identified using registers with comprehensive nationwide coverage. Hence, all eligible IVF/ICSI cycles among the entire female population in each country will be included and the results from the study are expected to be representative of that population.

Women aged 18 years or more at ovarian stimulation start during the study period will be identified as eligible for inclusion in the study from each country's IVF Register. Individual-level data will then be linked to the Prescribed Drug Register, the National Patient Register, and the Medical Birth Register to further determine eligibility and ascertain baseline characteristics and safety and pregnancy outcomes. More details on each register are provided in Section 9.4.

For inclusion, all stimulation cycles will be assessed on a set of inclusion and exclusion criteria. The overall study population will include all women with at least one IVF/ICSI stimulation cycle fulfilling all eligibility criteria. Analysis-specific selection criteria, depending on the outcome of interest, will also be applied (see Section 9.7.1).

For inclusion of a stimulation cycle in the study, women must fulfill all of the following inclusion criteria:

1. *Initiated IVF/ICSI stimulation cycle with rhFSH-alfa reference product, HP-hMG or rhFSH-alfa biosimilar product monotherapy for COS during the study period²*
2. *Aged 18 years or more at stimulation cycle index date*
3. *Female sex at stimulation cycle index date*

Stimulation cycles are not eligible for this study if any of the following exclusion criteria are fulfilled:

1. *History of 5 or more IVF/ICSI stimulation cycles prior to the stimulation cycle index date*
2. *Ovarian stimulation for the purpose of oocyte donation, oocyte storage, embryo donation, oncological or other medically indicated embryo storage³, or preimplantation genetic testing (PGT)*
3. *Non-availability of individual-level data on IVF/ICSI treatment, dispensed drugs and medical history for 36 months or more prior to and including the stimulation cycle index*

² For Sweden, inclusion of eligible women may be limited to 31 December 2019 because of Q-IVF data availability.

³ For Denmark, oncological/medically indicated embryo storage will be derived based on information on cancer and other relevant diagnoses and associated treatments recorded in the DIVF and other national registers. Relevant codes will be detailed in the SAP. For Sweden, this information is directly available in the Q-IVF.

date, operationalized as the woman not being resident of the country where the IVF/ICSI treatment was performed during the 36-month period

Study time periods and stimulation cycle index date are defined in Section 9.2.3.

9.2.2 Definition of Study Cohorts and Description of Treatments

Among the women included in the study, three study cohorts will be created at the level of the IVF/ICSI stimulation cycle based on which drug the woman received for COS: rhFSH-alfa reference product, HP-hMG or rhFSH-alfa biosimilar product. Only one type of gonadotropin use will be allowed for each stimulation cycle. Hence, cycles where mixed gonadotropin use was observed will not be included in the study. Mixed gonadotropin use may occur for example if, at prescription refill at the pharmacy, the drug (brand) on the written prescription was exchanged for an equivalent drug (same active substance, strength, formulation; therapeutically equipotent).

A woman may contribute maximum five stimulation cycles to the same cohort if she had several cycles with the same study drug. She may contribute cycles to more than one study cohort if she had distinct stimulation cycles with different study drugs. Between stimulation cycles with a study drug, a woman may have received a non-study gonadotropin for COS. History of IVF/ICSI treatment, including with a non-study gonadotropin, will be controlled for in the analysis (in the PS estimation). Overall, no more than five stimulation cycles and only up to the fifth stimulation cycle will be considered in this study, regardless if all cycles were observed in the study period and the type of gonadotropin used for COS.

FET cycles originated from an IVF/ICSI stimulation cycle included in the study will be assigned to the same cohort as that stimulation cycle. FET cycles originated from a stimulation cycle in which one of the study drugs was used but which was not included in the study (e.g., because of PGT), will not be considered. Different methods for cycle linkage will be used for Denmark and Sweden. For Sweden, the IVF register includes information enabling an FET cycle to be linked to the stimulation cycle it originated from. This information is the follicular aspiration date, which is recorded for IVF/ICSI stimulation cycles and FET cycles alike. For Denmark, no such direct link exists in the IVF register.

